1 INTRODUCTION

This Statistical Analysis Plan (SAP) describes the planned analysis and reporting for Arcutis Biotherapeutics, Inc. clinical protocol ARQ-151-311. The analyses described in the SAP are based upon the protocol Amendment 4 dated 28 September 2022. In case of changes (note that any such changes are described in section 3.5 below) between the protocol and the SAP, the SAP will be used to guide the statistical analysis. Any deviations from the SAP will be described and justified in the final Clinical Study Report (CSR), as appropriate.

On [REDACTED] FDA provided the following advice in preliminary feedback prior to a pre-NDA meeting held with Arcutis for a similar program on [REDACTED]

For the primary estimand, you [Arcutis] proposed a treatment policy strategy to handle all intercurrent events, including treatment discontinuation due to adverse event or lack of efficacy. For intercurrent events of treatment discontinuation due to adverse events or lack of efficacy, we [FDA] recommend a composite strategy policy where subjects will be defined as non-responders, as we consider this to be the appropriate approach for handling such events. Your proposal to handle intercurrent events of treatment discontinuation using the treatment policy strategy can be used as part of a supportive estimand.

The purpose of this version of the SAP is to document the change to the primary estimand and related multiple imputation strategies as requested by the FDA for a similar program.

This SAP has been developed prior to database lock, unblinding, and associated analyses. All final analyses will be performed after approval of the SAP, the clinical trial data are entered into the database, any discrepancies in the data are resolved, determination of the inclusion/exclusion of each subject from each analysis population, the database is locked, and the unblinding request form is signed.

2 STUDY OBJECTIVES AND ENDPOINTS

OBJECTIVES	ENDPOINTS
Efficacy	
To assess the efficacy of Roflumilast (also known as ARQ-151) cream 0.15% vs vehicle administered once daily	
Primary efficacy endpoint:
 
 • Validated Investigator Global Assessment scale for Atopic Dermatitis (vIGA-AD) Success, defined as a vIGA-AD score of 'clear' (0) or 'almost clear' (1)

	STATISTICAL ANALYSIS PLAN, Version 3.0
Protocol Number: ARQ-151-311	Sponsor: Arcutis Biotherapeutics, Inc.

OBJECTIVES	ENDPOINTS
(QD) x 4 weeks to individuals 6 years of age and older with atopic dermatitis (AD).	
plus at least a 2-grade improvement from Baseline at Week 4
 
Secondary efficacy endpoints:
 
 • In subjects with a vIGA-AD score of 'Moderate' at randomization, vIGA-AD Success at Week 4 • In subjects ≥ 12 years old with baseline Worst Itch - Numeric Rating Score (WI-NRS) ≥ 4, achievement of at least a 4-point reduction on the WI-NRS at Week 4 • In subjects ≥ 12 years old with baseline WI-NRS ≥ 4, achievement of at least a 4-point reduction on the WI-NRS at Week 2 • In subjects ≥ 12 years old with baseline WI-NRS ≥ 4, achievement of at least a 4-point reduction on the WI-NRS at Week 1 • Achievement of at least a 75% reduction in the Eczema Area and Severity Index (EASI-75) at Week 4 • vIGA-AD of 'clear' or 'almost clear' at Week 4 • vIGA-AD Success at Week 2 • vIGA-AD Success at Week 1 • vIGA-AD of 'clear' or 'almost clear' at Week 2 • vIGA-AD of 'clear' or 'almost clear' at Week 1 
Exploratory efficacy endpoints:
 
 • Other continuous efficacy endpoints include change and percent change in average weekly WI-NRS and daily WI-NRS, EASI, % body surface area (BSA) affected by AD, Dermatology Life Quality Index (CDLQI/DLQI), the Dermatitis Family Impact (DFI), Scoring Atopic Dermatitis (SCORAD), and Patient-oriented Eczema Measure (POEM) at Week 1, Week 2 and Week 4. • Other categorical efficacy endpoints include EASI-50, EASI-90, EASI-100, and vIGA-AD of 'clear' at Week 4
Safety	

	STATISTICAL ANALYSIS PLAN, Version 3.0
Protocol Number: ARQ-151-311	Sponsor: Arcutis Biotherapeutics, Inc.

OBJECTIVES	ENDPOINTS
To assess the safety of Roflumilast cream 0.15% vs vehicle administered once daily (QD) x 4 weeks to individuals 6 years of age and older with AD	
 Incidence and severity of adverse events (AEs) Changes and percent change in clinical laboratory results Changes and percent change in vital signs The subject incidence of >5% weight loss or gain on study Local tolerability assessments Patient Health Questionnaire depression scale (PHQ-8) and Modified PHQ-9 for Adolescents (PHQ-A) Children's Depression Inventory 2nd Edition (CDI-2) Columbia-Suicide Severity Rating Scale (C-SSRS)
Pharmacokinetic	
To assess the systemic exposure of roflumilast and its N-oxide metabolite following Roflumilast cream 0.15% QD application x 4 weeks	
 Plasma concentrations of roflumilast and its N-oxide metabolite

3 STUDY DESIGN

3.1 Overall Design

[figure not shown]
This is a Phase 3, parallel group, double blind, vehicle-controlled study in which Roflumilast cream 0.15% or vehicle is applied QD x 4 weeks to subjects with mild to moderate atopic dermatitis.

- Upon determination of eligibility, subjects will be randomized 2:1 to either Roflumilast cream 0.15% or matching vehicle cream. The randomization will be stratified by vIGA-AD score at baseline ('Mild' vs. 'Moderate') and by study site.
- At the Week 4 visit, subjects may be eligible to enroll in an open label extension study (ARQ-151-313) in which they will receive Roflumilast cream 0.15% QD.

The trial design is represented schematically in [Figure 1](#).

	STATISTICAL ANALYSIS PLAN, Version 3.0
Protocol Number: ARQ-151-311	Sponsor: Arcutis Biotherapeutics, Inc.

Figure 1 Study Schema

A Phase 3, 4-Week, Parallel Group, Double Blind, Vehicle-Controlled Study of the Safety and Efficacy of ARQ-151 Cream 0.15% Administered QD in Subjects with Atopic Dermatitis

Approximately 650 subjects with atopic dermatitis will be randomized 2:1 to receive either:

- Roflumilast cream 0.15% or Vehicle cream

Subjects will have $\geq 3\%$ BSA involvement (excluding the scalp, palms, soles) with a vIGA-AD score of '2' (mild) or '3' (moderate) for study entry

Up to 50% of the subjects will be ≥ 18 years old

	STATISTICAL ANALYSIS PLAN, Version 3.0
Protocol Number: ARQ-151-311	Sponsor: Arcutis Biotherapeutics, Inc.

3.2 Schedule of Events

Table 1 Schedule of Visits and Assessments

Study Procedure	Screen	Baseline Day 1	Wk 1 Day 8	Wk 2 Day 15	Wk 4 Day 29 / ET
Visit	1	2	3	4	5
Visit Window	-30 days	N/A	+/- 3 days	+/- 3 days	+/- 3 days
Informed consent/assent	X				
Demographics	X				
Medical and surgical history	X				
Physical examination ^a	X	X			X
I/E criteria	X	X			
Hematology, Serum Chemistries, and Urine Analysis ^b	X ^b	X ^b			X ^b
Vital signs, height, weight ^c	X	X	X	X	X
vIGA-AD, EASI, BSA, SCORAD ^d	X	X	X	X	X
WI-NRS pruritus ^e	X	X	X	X	X
POEM ^f	X	X	X	X	X
Local Tolerability Assessment ^g		X	X	X	X
CDI-2, PHQ-8, PHQ-A, C-SSRS ^h	X	X	X	X	X
DLQI, CDLQI, DFI ⁱ	X	X	X	X	X
Medical Photography ^j		X	X		X
Serum pregnancy test (FOCBP only)	X				
Urine pregnancy test ^k		X	X	X	X
PK draws ^l					X
Drug/vehicle application in clinic ^m		X	X	X	
Dispense/Re-dispense study medication kit ⁿ		X	X ^o	X ^o	X ^o
Dispense/review diary	X	X	X	X	X
Weigh study medication kit ^p		X	X	X	X
Compliance determination ^q			X	X	X

	STATISTICAL ANALYSIS PLAN, Version 3.0
Protocol Number: ARQ-151-311	Sponsor: Arcutis Biotherapeutics, Inc.

Study Procedure	Screen	Baseline Day 1	Wk 1 Day 8	Wk 2 Day 15	Wk 4 Day 29 / ET
Adverse event assessment ^r	X	X	X	X	X
Concomitant medications	X	X	X	X	X
Study Exit ^s					X

a Limited physical examination: skin (including assessment of Fitzpatrick skin type at Screening only), lungs, and heart only

b For all subjects entering this study under Amendment 2, to be collected at Screening, but subsequent samples will be collected only for subjects ≥ 12 years old (Baseline/Day 1 and Week 4/Day 29/ET). For subjects 12 to 18 years of age, if Baseline/Day 1 is within 3 weeks of Screening, the Screening results may be used.

c Height will be collected at Screening only. Weight should be obtained using a calibrated weight scale and the same scale should be used for a subject throughout the duration of the study. The subject should remove shoes and heavy clothing (sweaters or jackets), and empty pockets. The subject should stand with both feet in the center of the scale with their arms at their side and hold still. Record the weight to the nearest decimal fraction (for example, 25.1 kilograms). For subjects <18 years of age, measure the weight in triplicate and report the average weight in EDC. A 5% or greater weight loss (whether or not intentional or other explained) should be reported to the medical monitor.

d The vIGA-AD assessment will be a 5-point scale ranging from clear (0) to severe (4) and is evaluated for the entire body except the scalp, palms, and soles. EASI takes into account overall severity of erythema, infiltration/papulation, excoriation, and lichenification, in addition to extent of BSA affected. The 4 clinical signs will be graded on a 4-point scale (0 [absent] to 3 [severe]) for 4 body regions (head and neck, upper extremities, lower extremities, and trunk). Total EASI score will be calculated as a sum of scores of all 4 body regions. EASI total score will range from 0 (absent) to 72 (severe). Total BSA affected by AD will be determined for all body surfaces except the scalp, palms and soles. **The vIGA-AD assessment should be completed prior to other physician assessments.** SCORAD total score will range between 0 and 103.

e Subjects will self-assess their pruritus at home on a daily basis starting 7 days prior to the Baseline/Day 1 visit, and then every day thereafter. WI-NRS score will be determined by the subject assessing worst itch over the past 24 hours. The scale is from 0 (no itch) to 10 (worst itch) and this value will be recorded by the subject each day. Subjects will be trained at the Screening visit in the accurate completion of the WI-NRS. In addition, parents/caregivers of children and adolescent subjects will be trained at the Screening visit by study staff on how to assist the subject, if needed, in completing the WI-NRS.

f POEM will be completed by all subjects either by self or by proxy completion (for children unable to read and/or understand the POEM questionnaire, the parent/guardian/caregiver will complete the questionnaire).

g Local tolerability assessments should be recorded prior to study drug application for the Investigator assessment of skin irritation (Berger and Bowman skin irritation score). **Note for investigator tolerability assessments: reactions at the site of product application, which may occur post-Baseline, should be differentiated from the preexisting inflammation associated with the subject's atopic dermatitis.** The subject will assess burning/stinging (0-3 score) 10-15 minutes post drug application. **Note subject burning/stinging assessment: at Day 29, subjects will provide a recall assessment of burning/stinging experienced post drug application on the previous day (Day 28).**

h Adolescents and adults will complete the C-SSRS (12 years of age and older). Adults will complete the PHQ-8. Adolescents (ages 12 to 17, inclusive) will complete the PHQ-A (PHQ-9 modified). Parents/caregivers will complete CDI-2 (parent report) for children 6-11 years of age, inclusive.

i The DLQI will be completed by subjects ≥ 17 years of age. The CDLQI will be completed for subjects 6 to 16 years old, inclusive. The Dermatitis Family Impact Questionnaire (DFI) will be completed by parents/caregivers for all subjects 6 to ≤ 17 years of age.

j Photography of AD lesion(s) selected by the Investigator will be performed at all investigational sites. All efforts will be made to de-identify the subjects. Canfield equipment will be used to capture photographs. Subjects who are unwilling to participate in the medical photography will be allowed to opt out of this procedure, as documented on the Informed Consent Form.

	STATISTICAL ANALYSIS PLAN, Version 3.0
Protocol Number: ARQ-151-311	Sponsor: Arcutis Biotherapeutics, Inc.

^k A urine pregnancy test will be administered to all females of child-bearing potential. A negative result is required for continued participation in the study, and results must be available prior to dispensing of study drug at each visit.

^l For all subjects entering this study under Amendment 2, a single PK trough draw will be collected at Day 29 only for subjects \geq 12 years old. Ensure study medication was not applied in the area where PK will be drawn.

^m Subjects to apply assigned IP during clinic visits, except for the Day 29/ET visit.

ⁿ It is expected that kits will be dispensed based on %BSA affected. See IP Handling Manual for details.

^o On Day 8 and 15, dispensing of IP is optional. Site should review IP kit to ensure sufficient IP is available until the next visit and only dispense additional IP if needed. On Day 29, if the subject is unable to perform the Day 29 clinic visit due to COVID-19 restrictions (isolation, quarantine, etc.) then additional IP may need to be dispensed so IP can continue to be applied at home until the subject is able to return to the clinic to complete the Day 29 assessments (see IP Handling Manual for the process to dispense additional IP at or after Day 29).

^p Every tube should be weighed and recorded when dispensed and returned. See IP Handling Manual for details.

^q Compliance determination is described in the IP Handling Manual

^r All AEs should be collected starting after the first application of the investigational product through the end of the study. All SAEs should be collected starting after the signing of the informed consent through 30 days after the last day of the application of the investigational product or the end of the study (whichever is later). Any AEs (whether serious or non-serious) and clinically abnormal laboratory test values(s) will be evaluated by the PI and treated and/or followed up for up to 30 days after end of treatment or until symptoms or value(s) return to normal, or acceptable level, as judged by the PI (if the subject is continuing into the ARQ-151-313 OLE study, then AEs from this study (ARQ-151-311) will only be followed until exit from this study).

^s Subjects who enroll into the open label extension study (ARQ-151-313) must complete the ARQ-151-311 visit requirements at Week 4.

3.3 Treatment

Roflumilast cream 0.15% or vehicle cream will be administered QD for 28 days (+/- 3 days).

- Roflumilast cream 0.15%
- Vehicle cream

3.4 Randomization, Replacement, and Unblinding Procedures

Randomization will take place at the Baseline visit prior to first dosing. Subjects who meet all eligibility criteria will be randomized at a 2:1 ratio (drug:vehicle) to receive Roflumilast cream 0.15% QD or matching vehicle QD. The randomization will be stratified by vIGA-AD score at baseline ('Mild' vs. 'Moderate') and by study site according to a computer-generated randomization list. Kits containing tubes of study medication will be assigned to each subject using an internet-based response system (IWRS). A subject may receive more than one kit for the treatment period. The kits and tubes are blinded and each kit is numbered with a unique kit number.

The study is double-blinded, therefore neither the subjects nor the Investigator, sponsor and clinical personnel will be aware of which treatment an individual subject receives.

	STATISTICAL ANALYSIS PLAN, Version 3.0
Protocol Number: ARQ-151-311	Sponsor: Arcutis Biotherapeutics, Inc.

3.5 Changes to the Analysis from the Protocol

Rationale for change	Description of the change
A categorical summary was excluded from the SAP as it was determined that it was not necessary.	
Original text:
 
The amount of investigational product used by each subject based on tube weight will be summarized by treatment using descriptive statistics, and categorically.
 
Changed to:
 
The amount of investigational product used by each subject based on tube weight will be summarized by treatment using descriptive statistics.

To separate COVID patient from Per Protocol analysis set.	
Original text:
 
Per protocol (PP) population will include all subjects in the ITT population, who are at least 80% compliant with study medication application, and show no major deviations from the study protocol that would affect the interpretation of efficacy. In addition, subjects who miss the Week 4 vIGA-AD assessment specifically due to novel coronavirus disease-19 (COVID-19) disruptions will be excluded from per protocol population.
 
Changed to:
 
Per protocol population will include all subjects who are randomized, at least 80% compliant with study medication application, have a vIGA-AD assessment within the Week 4 visit window, and show no “major deviations” from the study protocol that would affect the interpretation of efficacy.

Added mITT population to address COVID-19 impact.	The mITT population includes all randomized subjects with the exception of subjects who missed the week 4 vIGA-AD assessment specifically due to COVID-19 disruption. This population will be used for sensitivity analysis for the primary endpoint.

	STATISTICAL ANALYSIS PLAN, Version 3.0
Protocol Number: ARQ-151-311	Sponsor: Arcutis Biotherapeutics, Inc.

4 POPULATIONS FOR ANALYSIS

4.1 Intent-to-Treat (ITT) Population

Intent-to-Treat population will include all subjects who are randomized, and all subjects will be analyzed according to the treatment group and stratum to which they were randomized.

4.2 Modified Intent-to-Treat (mITT) Population

The mITT population includes all randomized subjects with the exception of subjects who missed the week 4 vIGA-AD assessment specifically due to COVID-19 disruption. This population will be used for sensitivity analysis for the primary endpoint. All subjects will be analyzed according to the treatment group and stratum to which they were randomized.

4.3 Per Protocol (PP) Population

Per protocol population will include all subjects who are randomized, at least 80% compliant with study medication application, have a vIGA-AD assessment within the Week 4 visit window and show no “major deviations” from the study protocol that would affect the interpretation of efficacy. A complete list of major deviations from the study protocol will be created prior to unblinding and include a list of all subjects who will be excluded due to those major deviations. See section [7.2](#) for more details.

All subjects will be analyzed according to the actual treatment group they received and the stratum they belong to. Actual and randomized treatment will only differ if the subject received the wrong treatment throughout their participation in the study.

4.4 vIGA-AD Moderate ITT Population

vIGA-AD Moderate ITT population will be a subset of the ITT population with vIGA-AD score (randomized score) ‘Moderate’ at randomization.

All subjects will be analyzed according to the treatment group and the stratum to which they were randomized.

4.5 vIGA-AD Moderate PP Population

vIGA-AD Moderate PP population will be a subset of the PP population with vIGA-AD score (actual score) ‘Moderate’ at randomization.

	STATISTICAL ANALYSIS PLAN, Version 3.0
Protocol Number: ARQ-151-311	Sponsor: Arcutis Biotherapeutics, Inc.

All subjects will be analyzed according to the actual treatment group they received and the stratum they belong to. Actual and randomized treatment will only differ if the subject received the wrong treatment throughout their participation in the study.

4.6 WI-NRS Population

WI-NRS population will be a subset of the ITT population among subjects ≥ 12 years old with average weekly baseline WI-NRS score ≥ 4 .

The subjects in WI-NRS population are those:

1. Completed at least 4 of 7 evaluable daily WI-NRS questionnaires during the last 7 days of the Screening period;
2. Have a mean baseline WI-NRS score ≥ 4.0 , defined as the average of all non-missing scores reported during the last 7 days of the Screening period if at least 4 of 7 evaluable daily WINRS questionnaires available. If 4 or more evaluable daily questionnaires are missing, then the data will be treated as missing.

All subjects will be analyzed according to the treatment group and stratum to which they were randomized.

4.7 Safety Population

Safety population will include all subjects who are enrolled and received at least one confirmed dose of study medication.

Subjects will be analyzed based on the treatment group received and the stratum they belong to. Actual and randomized treatment will only differ if the subject received the wrong treatment throughout their participation in the study.

4.8 Pharmacokinetic (PK) Population

Pharmacokinetic population will include all subjects receiving the active drug with quantifiable plasma concentrations of roflumilast.

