5.4 Windowing Conventions

Visits will be analysed as scheduled. Unscheduled, early termination visits, and/or retest measurements will only be included if a scheduled measurement is not available and the early termination or unscheduled/retest measurement falls within the analysis visit windows as described in [Table 2](#), [Table 3](#), and [Table 4](#) when appropriate. Unscheduled/retest measurements will be listed.

If there is more than one assessment for a given timepoint and analysis visit when a scheduled measurement is not available, the assessment closest to the target day will be considered.

	STATISTICAL ANALYSIS PLAN, Version 3.0
Protocol Number: ARQ-151-311	Sponsor: Arcutis Biotherapeutics, Inc.

Table 2 Analysis Visit Windows for Efficacy Endpoints, Vital Signs, CDI-2, PHQ-8, PHQ-A, C-SSRS and Local Tolerability Assessment

Analysis Visit	Target Day	Lower Limit	Upper Limit
Week 1	8	2	11
Week 2	15	12	22
Week 4	29	23	43

Table 3 Analysis Visit Windows for Clinical Laboratory, Physical Examination and PK assessment

Analysis Visit	Target Day	Lower Limit	Upper Limit
Week 4	29	23	43

Table 4 Windows for the derivation of Average Weekly WI-NRS

Days for calculation of weekly average	Week (Derived)
(-7, -1)*	Baseline
(1, 7)*	Week 1
(8, 14)	Week 2
(15, 21)	Week 3
(22, 28)	Week 4

* Day 1 WI-NRS score will be used to calculate the value for week 1 only when it is collected after the application of the first study drug (randomization for randomized subjects who were never treated with study drug). If Day 1 WI-NRS score is collected prior to or concurrently with the application of the first study drug (randomization for randomized subjects who were never treated with study drug), then the Day 1 WI-NRS score will be included in baseline calculation.

Note: With the caveat described in footnote **, if more than one WI-NRS score is available on the same day, the worst score of the day will be considered in the analyses.

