5.6 Descriptive Statistics

All continuous variables will be summarized by presenting the number of subjects, mean, standard deviation (SD), median, Q1, Q3, minimum, and maximum. For PK endpoints, geometric statistics including geometric mean and coefficient of variation (CV) will also be provided.

Categorical variables will be presented as frequencies and percentages.

Summary tables will be presented by visit, when applicable.

Change from baseline will be calculated as:

	STATISTICAL ANALYSIS PLAN, Version 3.0
Protocol Number: ARQ-151-311	Sponsor: Arcutis Biotherapeutics, Inc.

Assessment value at postbaseline visit X – baseline value.

Percent change from baseline will be calculated as:

$$(\text{Assessment value at postbaseline visit X} - \text{baseline value}) \times 100\% / (\text{baseline value})$$

Percent change from baseline will be missing in situation where baseline value equals to 0.

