14 PHARMACOKINETICS ANALYSIS

Concentration data will be summarized by visit by age group (<18 vs. ≥ 18) and overall, for active treatment group using descriptive statistics, reporting n, mean, standard deviation, median, Q1, Q3, minimum, and maximum, and geometric statistics including geometric mean and coefficient of variation. For computation of mean plasma concentrations, data that are below the limit of quantification (BLQ) will be set to 0.0001. The PK population will be used for these analyses.

PK data will be presented in the listing.

	STATISTICAL ANALYSIS PLAN, Version 3.0
Protocol Number: ARQ-151-311	Sponsor: Arcutis Biotherapeutics, Inc.

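### The PK population drops every planned roflumilast result below the quantification limit, so the roflumilast summary describes only subjects with quantifiable drug

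*SAP*

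**What the plan says.** - **Objective and endpoint (SAP 2).** The PK objective is "To assess the systemic exposure of roflumilast and its N-oxide metabolite following Roflumilast cream 0.15% QD application x 4 weeks". The endpoint is "Plasma concentrations of roflumilast and its N-oxide metabolite", so there are two analytes.
- **Sampling (SAP 3.2, footnote l).** For subjects entering under Amendment 2, "a single PK trough draw will be collected at Day 29 only for subjects" aged 12 or older. Protocol 5.3.4 (the supplied original version) plans one trough at Week 4/Day 29 in every subject.
- **Population (SAP 4.8).** "Pharmacokinetic population will include all subjects receiving the active drug with quantifiable plasma concentrations of roflumilast". Protocol 6.3 and the protocol synopsis give the same definition.
- **Windowing (SAP 5.4).** Table 3, "Analysis Visit Windows for Clinical Laboratory, Physical Examination and PK assessment", has a single analysis visit, Week 4, running from Day 23 to Day 43. Where no scheduled measurement exists and several others fall in the window, the one closest to the target day is used.
- **Analysis (SAP 14).** Concentrations are summarised for the active arm, overall and by age group (under 18, and 18 or older), with arithmetic and geometric statistics. For the computation of means, "data that are below the limit of quantification (BLQ) will be set to 0.0001". The section then says: "The PK population will be used for these analyses". SAP 5.6 repeats the geometric part: "For PK endpoints, geometric statistics including geometric mean and coefficient of variation (CV) will also be provided".

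**The concern.** A subject enters the PK set only if the quantity being summarised is high enough to be measured. That is selection on the outcome, and it has three consequences.

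1. The roflumilast statistics describe exposure among subjects with quantifiable drug. That is narrower than the stated objective, and for the mean, median, quartiles and geometric mean the difference can go only one way, upward.
2. The N-oxide summary loses every subject whose parent drug is BLQ, even where that subject's N-oxide was measurable. The direction of this effect is not known.
3. SAP 14 plainly expects BLQ data and gives a rule for them, but SAP 4.8 removes all such planned values for the parent drug before the rule can apply. The substituted 0.0001 also has no unit, and the SAP does not say outright whether it is used for the geometric mean and CV.

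If BLQ rates differ between the two age groups, the groups are also truncated to different degrees.

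**Working it through.** **Step 1: how many roflumilast BLQ values can reach the summary.** There is one planned draw per sampled subject (SAP 3.2; Protocol 5.3.4). If that draw is BLQ for roflumilast, the subject has no quantifiable roflumilast value and fails SAP 4.8. SAP 14 uses only the SAP 4.8 set. The number of planned roflumilast BLQ values in the summary is therefore 0, whatever the BLQ rate. An extra retest or unscheduled sample is the only way round this, and none is planned. The 0.0001 rule is left with N-oxide values that are BLQ in subjects whose parent drug is quantifiable.

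**Step 2: inputs for size.** The plan states no figure to reproduce. The BLQ share *q* and the lower limit of quantification (LLOQ) are not in the supplied documents, so *q* = 1%, 5%, 10% and 20% are assumed. For scale, 650 × 2/3 = 433 subjects are planned on active drug. If all were sampled, *q* = 5%, 10% or 20% would remove about 22, 43 or 87. The sampled number is lower, because subjects under 12 entering under Amendment 2 give no Day 29 sample.

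**Step 3: bound on the arithmetic mean.** Counting BLQ values as 0, the mean over all sampled subjects is (1 − *q*) times the quantifiable-only mean, so inflation is at most 1/(1 − *q*).

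**Step 4: lognormal illustration.** Assume lognormal concentrations with log-SD σ and remove the lowest fraction *q*. With z_q the standard normal *q*-quantile, the ratios to the full distribution are:

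- mean: Φ(σ − z_q)/(1 − *q*)
- median: exp(σ·Φ⁻¹(*q* + (1 − *q*)/2))
- geometric mean: exp(σ·φ(z_q)/(1 − *q*))

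| *q* | Upper bound, mean | Mean (σ = 1) | Median (σ = 1) | Geometric mean (σ = 1) |
|---|---|---|---|---|
| 1% | 1.010 | 1.010 | 1.013 | 1.027 |
| 5% | 1.053 | 1.048 | 1.065 | 1.115 |
| 10% | 1.111 | 1.099 | 1.134 | 1.215 |
| 20% | 1.250 | 1.209 | 1.288 | 1.419 |

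Sensitivity at *q* = 10%: with σ = 0.7 the mean, median and geometric-mean ratios are 1.085, 1.092 and 1.146; with σ = 1.5 they are 1.108, 1.207 and 1.340. Spread is affected too: at *q* = 10% and σ = 1, the geometric CV falls from 131% to 102%.

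**Step 5: what happens if only the population is widened.** Let R = LLOQ/0.0001 in the same unit (assumed, since no unit is given). Using 0.0001 in place of the LLOQ multiplies the geometric mean by R^(−*q*). At *q* = 10% this is 0.794 for R = 10, 0.631 for R = 100 and 0.501 for R = 1000. With σ = 1, the geometric CV would be 242% at R = 10 and 721% at R = 100, against 138% with LLOQ/2 and a true 131%. These figures do not describe the present roflumilast summary. They show that a change to SAP 4.8 alone would replace one distortion with another.

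**The case against.** The strongest reply is that this is a prespecified choice, worded identically in the supplied protocol and the SAP, for a purely descriptive summary. The BLQ rule still has a use, because the N-oxide is a named analyte. No BLQ rate is known, so no effect has been shown in this trial, and overstating roflumilast exposure would not hide exposure. Some transparency is already planned: SAP 7.1 gives population counts, SAP 8 lists the population flag and SAP 14 lists the PK data. A BLQ percentage may also appear in the table layouts, which SAP 5 places in a separate document that was not supplied.

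Most of these facts stand, and they limit the weight of the point. They do not remove it. Repeating a definition does not stop it selecting on the outcome, and listings and counts do not correct the summary statistics.

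A second reply is that the Day 23–43 window, together with the inclusion of early-termination data (SAP 5.8), may bring in BLQ results from subjects who had already stopped applying the cream. Counting these may not describe 4 weeks of use any better. That is fair, but the present definition has the same weakness: it admits off-treatment samples whenever they are quantifiable. Time since last application can be handled directly; detectability is a poor substitute for it.

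**Conclusion.** The concern holds. Followed exactly, the SAP leaves no planned roflumilast BLQ value in its PK summary, and the BLQ rule in SAP 14 has no effect on the parent drug. Roflumilast averages are overstated or unchanged relative to all sampled active subjects. For the N-oxide, data are lost because of another analyte, with no known direction.

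The size depends on a BLQ share that the documents do not give, and it is zero if no sample is BLQ. Over assumed shares of 1% to 20%, the arithmetic mean is inflated by at most 1% to 25%. With log-SD 1, also assumed, the geometric mean is inflated by 3% to 42%. Efficacy, alpha and power are not affected. The change should be made, but the trial's conclusions on efficacy do not depend on it. The logical step is certain; how much it matters in practice is not known.

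**What to change.** 1. **SAP 4.8:** define the PK population as active-treated subjects with a valid Week 4 plasma result in the Table 3 window, whether quantifiable or BLQ. Say what makes a result valid. If samples taken after treatment has stopped are a worry, address them through time since last application, not through the measured concentration.
2. **SAP 14:** report the number and percentage BLQ for each analyte and age group.
3. **SAP 14:** state one BLQ rule, with its unit, for both arithmetic and geometric statistics, and tie it to the assay LLOQ. The exact fraction is the sponsor's choice. This must change together with item 1, for the reason shown in Step 5.
4. **SAP 3.5:** record the change; the section now lists three changes and none concerns PK. Check the wording against protocol Amendment 4, on which the SAP is based. The supplied protocol is the original version, so the current protocol text has not been seen.

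The cost is wording in three SAP sections, one check against the amendment and one programming change. The downside is that reported average roflumilast exposure may come out lower.
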